- Complete a questionnaire about symptoms of paranoia and sexual functioning
- Complete a test onability to recognize emotions called the Penn Emotion Recognition Test (ER-40).

Additionally at Visit 8 (week 6 or Early Termination);

- Complete a series of activities which will be used to measure process of thought called the CMINDS® and MSCEIT™ ME
- Have an additional blood sample taken (about 1 tablespoon) to monitor study drug levels in the blood
- EEG paradigm will be conducted

Follow Up Call

The volunteer will be asked to contact the study site one week after the last study drug dose to report taking any new medications or any unusual experiences since stopping the study drug.

Administration and dispensing of the study medication:

Except the one time challenge dose, this is a double-blind study, participants will be randomized to receive one of three possible intranasal study medications adjunctive to their antipsychotics: oxytocin 84 IU, oxytocin 168 IU or placebo (vehicle without oxytocin). Randomization will be performed stratifying gender groups, type of antipsychotic (typical versus atypical) and severity of symptoms based upon PANSS score (<90 versus >90) so that gender, symptom severity and antipsychotic type are distributed relatively evenly across treatment groups. Bottles containing placebo or two different concentrations of oxytocin will be formulated (See Study Drug Formulation below) so that the concentration of oxytocin in the high dose (168 IU) will be double that of the low dose (84 IU). All subjects will be instructed to spray 7 pumps of the spray bottle (one in each nostril, alternating nostrils) to achieve correct dose in the morning and again in the afternoon. Subjects will be given enough study drug at the time of the visit to last until the next visit with extra to cover approximately three additional days. Each pump bottle has 5 ml (300 IU) which is enough for 2.5 days of study drug. Therefore, subjects will be given one spray bottle supply at the time of each visit. The weight of each bottle will be recorded prior to dispensing. After all procedures are performed on baseline visit and study drug is randomly assigned, a dose of the study drug will be taken at the study site, in the presence of a staff member to insure correct administration.

Study Drug Compliance

- 1. Subjects will be instructed on proper use of the nasal device from study staff.

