- 2. Subjects will be given a diary card by the study staff to mark each use of the study drug in between site visits to the study site. This is to help subjects track study drug use. Subjects will be instructed to return study drug nasal spray bottles, used or unused, to the site at each visit along with the diary card.
- 3. Each bottle will re-weighed after return to estimate the amount of fluid remaining

STUDY DRUG:

Intranasal oxytocin is FDA approved as a lactation aid and was commercially marketed (Syntocinon®, Novartis) in the US up to the 1990's. It continues to be marketed commercially by Novartis in Europe and elsewhere. Oxytocin powder (Pictocin, Novartis) is readily available in the US and is used for intravenous

administration as a paruition stimulant in pregnant women. Both intravenous and intranasal oxytocin are well tolerated and safe (Hoover RT 1971) (see risk section of this Research Plan).

This study will use oxytocin powder supplied by Spectrum Laboratories and UCSD Investigational Drug Service (IDS) will make formulate both the Oxytocin and Placebo.

-Chlorbutanolhemihydrat 2.5mg -Methyl-4-hydroxybenzoat 0.4mg -Propyl-4-hydroxybenzoat 0.2mg -Dinatriumphosphatanhydricum 1.9mg -Acidumcitricumanhydricum 2.56mg 5.0mg -Na-Sorbit -Sorbitol 70% 25.0 mg -Glycerin 85% 25.0mg -Aqua pur. q.s.

Comment: 1 IU is 1.7 micrograms oxytocin and 1 puff is 12 IU (=20.4 micrograms oxytocin)

STATISTICAL CONSIDERATION

Our primary analysis will be the comparison of subjects on oxytocin with subjects on placebo using a mixed model repeated measures analysis (MMRM). If this comparison is statistically significant then we use a linear contrast to investigate the dose-response between 84 IU (42 IU bid) and 168 IU (84 IU bid). We also have introduced an adaptive design that is consistent with FDA guidance for phase 2 studies when dosing groups are unclear (2010).

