Futility Interim Analysis Plan. This randomized, double-blind study adopts an adaptive design with a single pre-specified, planned, unblinded interim analysis for futility stopping based on conditional power (CP) (stochastic curtailing method) (Halperin et al., 1982; Lan et al., 1982) or an equivalent stopping boundary on interim Z-test value (B-value) (Lan and Witts, 1988). The purposes of this formal interim analysis are to assess CP levels which are the probability of reaching statistically significant treatment difference at study end given the interim results. To avoid inflation of Type I error, no early stopping for efficacy is planned in this study. The unblinded data will be only available to external statistician [name] and not the PIs or other study staff.

It is well known that futility termination will reduce the Type I error rate (alpha) and inflate the Type II error rate (beta =1 minus power of the test), with the level of beta inflation bounded by P_{L0} , the probability of stopping for futility under the null hypothesis of no treatment effect (Lan et al., 1982; Lachin 2005). In order to maintain the design Type I error rate (alpha) at 5% and power close to 85%, we use an iterative procedure to determine the CP utility boundary values and the adjusted Z-test critical value in the final analysis, with 60% (P_{L0}) chance of stopping for futility under the null hypothesis. This provides: 1) a CP futility stopping boundary value equal to 0.3 at 50% enrollment (i.e. stop the trial if CP observed < 0.3) under the original design assumption (see Sample Size Calculation), 2) an adjusted Z-test critical value of 1.947 (ZF) for declaring significant treatment effect in the final analysis (or $P \le 0.0515$), and 3) an overall power of 84.6%, i.e. 15.4% overall Type II error rate with 3.1% false negative error rate at interim look and 12.3% probability of continuing the trial and failing to reject the null hypothesis (false negative error rate) at study end.

In summary, we provide the following futility stopping rule for assessing interim results at 50% enrollment:

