Analysis Methods: The primary population for efficacy analyses includes all randomized subjects based on the intention-to-treat principle. The population for safety analyses will include all subjects who receive at least one dose of study medication. In the primary analysis, we test the hypothesis of difference in PANSS total change score (Week 6) between the combined oxytocin and placebo groups with adjustment for baseline score using a likelihood-based mixed-effects model for longitudinal data analysis (MMRM LDA) (Fitzmaurice and Ware, 2004). The MMRM LDA model can accommodate incomplete data under the assumption of ignorable attrition (see below under Missing Data). The same MMRM LDA model will be applied to evaluate the dose-response relationship using a linear contrast for the placebo and oxytocin dose groups, comparisons of treatment groups over time using treatment-by-visit (categorical visit variable) interaction term, and the trajectories of treatment responses over time based on time slope computed for each subject (continuous time variable).

Secondary efficacy measures will be the PANSS positive symptom and negative symptom subscales, PANSS general psychopathology subscale, CGI-S, CGI-I HAM-A, CCDS, GAF, cognitive scales as with the primary endpoint using the same MMRM LDA analyses. No multiplicity adjustment will be made in the secondary analyses. Appropriate descriptive statistics with 95% confidence intervals will be provided within and across treatment groups. Normal assumption will be checked and nonparametric alternatives will be considered if the assumption is seriously violated.

Mediators and baseline moderators of treatment effects on efficacy outcome measures will also be explored (Kraemer et al., 2006). The significance of moderator effects due to baseline characteristics (age, gender, initial

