PANSS scores, duration of illness, class of medication) will be tested using treatment-by-baseline characteristic interaction terms in the MMRM LDA and/or ANCOVA models. To assess impact of improvement in one domain (e.g. positive symptoms) on the efficacy of a related symptom domain (e.g. negative symptoms), a mediator analysis model with terms for treatment, baseline, and positive symptoms improvement will be applied to determine significance of oxytocin effect on reductions in negative symptoms after adjustment for potential positive symptom improvement. We will perform similar mediator analysis for assessing inter-relationships between cognitive improvement and symptom improvement in positive and/or negative symptoms. In addition, cross-sectional baseline and longitudinal change score associations between treatment outcome measures and mediator effects will be assessed by including mediators as time-varying covariates in the MMRM LDA models (Diggle et al., 2001).

MU-Suppression. Data will be analyzed in two ways. Pearson rank correlations will be used to examine correlations between mu wave suppression in response to a single dose of OT and symptom severity at the end of 6 weeks of treatment. In additional exploratory analyses, mu suppression values will be split at the median into High suppressors and Low suppressors and followed up by correlations with symptom measures to determine if initial high suppression is correlated with greater improvement in symptom severity. Secondarily, Pearson rank correlations will be conducted between mu wave suppression and symptom severity at baseline, and between mu wave suppression and symptom severity after administration of a single dose of oxytocin.

Safety Endpoints. The safety dataset will contain all subjects who take at least one dose of oxytocin. All adverse events will be coded using the most current version of the Medical Dictionary for Regulatory Activities (MedDRA). The number and percentage of subjects reporting treatment-emergent adverse events will be tabulated within each dose group by treatment, system organ class (SOC) and MedDRA-preferred term. Treatment-emergent adverse events will be those adverse events that begin or worsened following the first dose of study drug. Adverse events will be further classified by severity and investigator-assigned relationship to study drug.

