Clinical laboratory values and vital signs measured at the end of each treatment period will be analyzed using ANOVA, with factors sequence, period and treatment. Dose-response relationships will be explored and any laboratory values that fall outside normal ranges will be identified.

Missing Data. Some observations may be missing after baseline assessment. Individual missing items in all scales will not be imputed. All subjects expressing the desire to discontinue the study will be asked to come in for a final assessment, prior to stopping their medications. The primary analysis will be based on the likelihood based mixed-effects model (MMRM LDA) which provides valid estimates of treatment effect under the missing at random (MAR) assumption. The assumptions about random dropout and MAR can be tested using methods proposed by Diggle et al. (2001) and dropout cohort visualization as in Potkin et al, (2009). Two sensitivity analyses will be conducted to evaluate the robustness of results: one based on a mixed-effects model for missing not at random (MNAR) data with covariate adjustment for dropout measures (Wu and Follmann, 1999; Wu et al., 2001), and the other based on the usual LOCF-ANCOVA method with missing data following dropout imputed by an individual's last observed measurement. Further details are provided in the Statistical Analysis Plan, which will clearly specify the mixed-effects model methodology, sensitivity analyses, and evaluation of the assumptions.

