10. HUMAN SUBJECTS

The proposed study will involve participants meeting DSM-IV-TR criteria for Schizophrenia. After completing a screening process, eligible participants will complete weekly study visits during a 7 week time period.

Approximately 71 subjects will be entered into the study at this site. Patients will be recruited from the outpatient services at UCSD Medical Center, a large program with over 2000 active patients and serving a large area in mid-town San Diego. Participants will be 21 years and older and will be in good general health.

Subjects will be selected according to the following inclusion/exclusion criteria:

Inclusion Criteria:

- 1. Adult men or women, 21 years of age or older.
- 2. Meet DSM-IV criteria for Schizophrenia
- 3. Women of childbearing potential must test negative for pregnancy at the time of enrollment based on urine pregnancy test and agree to use a reliable method of birth control during the study.
- 4. Must be on a therapeutic dose of 1 or 2 atypical or typical antipsychotic medications (for example, but not limited to: Clozapine, Olanzapine, Risperidone, Ziprasidone, Aripiprazole, Seroquel) with no major dose changes for at least 4 weeks.
- 5. A minimum PANSS total score of 55 at baseline and a score of at least 4 (moderate) on the subscale of the PANSS (suspiciousness/persecution) at screening.
- 6. Have a Clinical Global Impressions-Severity (CGI-S) scale score of at least 4 (moderately ill) at baseline.
- 7. Must be able to communicate effectively with the investigator and study coordinator and have the ability to provide informed consent.
- 8. Must be able to use nasal spray.
- 9. Must demonstrate an acceptable degree of compliance with medication and procedures in the opinion of the investigator.

Exclusion Criteria:

Subjects will be excluded from the study of they meet any of the following criteria:

- 1. Are pregnant or are breastfeeding
- 2. A urine drug screen performed at screening must not show evidence of recent use of drugs of abuse
- 3. Any active medical condition that in the opinion of the investigator will interfere with the objectives of the study
- 4. Are unsuitable in any way to participate in this study, in the opinion of the investigator.
- 5. Another current DSM-IV diagnosis other than Schizophrenia

Vulnerable populations will not be involved in this study.

Permitted:

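### Randomisation is stratified by gender and antipsychotic type, but the stated primary model adjusts only for baseline PANSS

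*Combined protocol and SAP*

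**What the plan says.** All the relevant text but one inclusion criterion is in Section 9 of the combined protocol and SAP.

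- **Randomisation** (Administration and dispensing of the study medication): "Randomization will be performed stratifying gender groups, type of antipsychotic (typical versus atypical) and severity of symptoms based upon PANSS score (<90 versus >90"). The stated purpose is to spread these characteristics evenly over the arms.
- **Primary analysis, first description** (Statistical Consideration): a "comparison of subjects on oxytocin with subjects on placebo using a mixed model repeated measures analysis (MMRM"). No covariates are given.
- **Primary analysis, full description** (Analysis Methods): the Week 6 change in PANSS total is compared "between the combined oxytocin and placebo groups with adjustment for baseline score using a likelihood-based mixed-effects model for longitudinal data analysis". Baseline score is the only covariate. The secondary outcomes use the same model.
- **Exploratory moderators** (Analysis Methods): gender is on the list of possible moderators, and the end of that list shows how they are examined: "PANSS scores, duration of illness, class of medication) will be tested using treatment-by-baseline characteristic interaction terms". This is the only place where gender and medication class enter a model.
- **Deferral** (Missing Data): "Further details are provided in the Statistical Analysis Plan, which will clearly specify the mixed-effects model methodology". The supplied text contains no such further specification.
- **Final test** (Futility Interim Analysis Plan): "an adjusted Z-test critical value of 1.947 (ZF) for declaring significant treatment effect in the final analysis".
- **Eligibility** (Section 10, inclusion criterion 4): "Must be on a therapeutic dose of 1 or 2 atypical or typical antipsychotic medications".

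**The concern.** Stratifying makes the arms more alike on gender and antipsychotic type than chance would. If these factors predict the PANSS outcome, the true variability of the treatment difference falls. A model that leaves them out does not register this: it keeps the variance they explain in the error term and reports too large a standard error. The result is a conservative test and lost power, not bias or an inflated false-positive rate.

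Severity is not part of the problem, because continuous baseline PANSS carries more information than a split at 90. The exploratory interaction tests do not help, because they put nothing into the primary model.

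There is also a pre-specification point. The covariates of the interim Z-test are not stated, and the final list of fixed effects is left to a further document. Naming the terms now closes that choice.

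**Working it through.** **Inputs from the plan.** 48 oxytocin and 24 placebo patients; d = 0.3; six AR(1) measurements with correlation 0.5; final critical value 1.947.

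**Assumptions not in the plan.** R² is the share of variance remaining after baseline PANSS that gender and antipsychotic type explain together. It is taken as 0, 2, 5 and 10%. Effects are standardised to the SD remaining after baseline. The Week 6 figures assume that d = 0.3 applies at that visit.

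**Step 1: the plan's critical value.** 2 × (1 − Φ(1.947)) = 0.0515, as stated.

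**Step 2: standard error and type I error under perfect balance.** The baseline-only standard error exceeds the adjusted one by the factor 1/√(1 − R²). The stand-alone two-sided type I error is 2 × (1 − Φ(1.947/√(1 − R²))).

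| R² | SE ratio | Type I error, baseline-only |
|---|---|---|
| 0% | 1.000 | 0.0515 |
| 2% | 1.010 | 0.0492 |
| 5% | 1.026 | 0.0458 |
| 10% | 1.054 | 0.0401 |

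**Step 3: Week 6 power under perfect balance.** The variance factor is 1/48 + 1/24 = 0.0625, so the standard error is 0.25 and d/SE = 0.3/0.25 = 1.2. Noncentral t with alpha 0.0515, on 69 df (baseline-only) and 67 df (adjusted), gives:

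- R² 0%: 22.3% baseline-only, 22.3% adjusted
- R² 2%: 22.1%, 22.7%
- R² 5%: 21.7%, 23.2%
- R² 10%: 21.1%, 24.3%

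**Step 4: imperfect balance.** Eight strata and 72 patients leave incomplete blocks, so 40,000 trials were simulated. The design was permuted blocks of 6 (2:1) within strata, with assumed prevalences of 35% in one gender group, 15% on typical agents and 25% above the PANSS cut. The analysis was a single-outcome ANCOVA with and without the two factors.

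| R² | Type I, baseline-only | Type I, adjusted | Power at d = 0.3, baseline-only | Power at d = 0.3, adjusted |
|---|---|---|---|---|
| 0% | 0.0518 | 0.0513 | 22.3% | 22.0% |
| 2% | 0.0499 | 0.0513 | 22.1% | 22.3% |
| 5% | 0.0473 | 0.0513 | 21.8% | 22.9% |
| 10% | 0.0429 | 0.0513 | 21.4% | 24.0% |

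The mean standard error at R² = 10% was 0.2504 without the factors and 0.2384 with them.

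A separate simulation with blocks of 3, 20% on typical agents, 30% above the cut and a nominal 0.05 test gave type I error of 0.041 without the factors and 0.050 with them at R² = 10%. The direction and approximate size are the same.

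**Step 5: near the plan's intended power.** At d = 0.75 (20,000 trials), power without and with the factors was 83.8% and 83.5% (R² = 0), 84.8% and 85.7% (5%), and 85.2% and 87.4% (10%).

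**Step 6: the time-averaged effect used for the sample size.** The variance factor is [6 + 2Σ(6 − k)0.5^k]/36 = 0.3906, with k from 1 to 5. Noncentral t power at R² = 10% rises from about 48% to about 52%, a gain of about 4 points. The starting value of about 48% is not the plan's 85%: with two-sided alpha 0.05, the plan's own inputs give 48.4%. That discrepancy is a separate matter and does not bear on this point.

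**The case against.** The strongest objection is that the plan defers the mixed-model methodology to a Statistical Analysis Plan, so silence in the protocol narrative does not show that the factors will be left out. That is fair, and nothing here claims they will be. But Analysis Methods does state an adjustment, and nothing in the supplied text extends it. If the detailed specification already lists the factors, bringing this section into line takes one sentence.

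Second, the gain depends on an R² the documents do not give. At 2% explained, simulated Week 6 power moves by about a quarter of a point. This stands, and it is why the result is given as a range that includes zero.

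Third, the simulations use a single-outcome ANCOVA. In a repeated-measures model, main effects adjust the Week 6 contrast only partly if a factor's effect varies by visit. Full adjustment would then need factor-by-visit terms and more than two degrees of freedom. This stands as a limit on the size of the gain, not on its direction.

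Fourth, the type I error figures treat 1.947 as a stand-alone test. If the futility stop at interim Z of 0.253 is followed as binding, the two-sided error is about 0.025 at R² = 0 and 0.020 at R² = 10%. The absolute values change, but the conservatism does not.

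Fifth, no figure has been computed for the interim model. With an assumed 15% on typical agents, about 5 of 36 patients (0.15 × 36 = 5.4) would inform that term. The reason for using the same model at the interim is consistency, not a demonstrated gain there.

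**Conclusion.** The concern holds as a small efficiency and pre-specification point. The stated primary model omits two of the three randomisation factors, and the third is covered by baseline PANSS. The test is valid and unbiased without them.

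For R² between 0 and 10%, the standard error is 0 to 5% too large. The stand-alone type I error at 1.947 runs from 0.0515 down to 0.040 under perfect balance, or to 0.043 with realistic imbalance. Adjusting ranges from a loss of under half a point of power to a gain of about 2 to 3 points at Week 6 and about 4 points for the time-averaged effect. These sizes rest on the assumed R², stratum prevalences and block size. The direction does not, provided the factors have some prognostic value.

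**What to change.** In Analysis Methods, state that the primary MMRM contains continuous baseline PANSS plus gender and antipsychotic type, as randomised, as fixed effects. State also that the interim Z-test uses the same model. The secondary outcomes inherit it through the existing wording. If effects that differ by visit are expected, say in advance whether factor-by-visit terms are included.

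Two minor clarifications in the randomisation text would let the strata be coded without ambiguity. As printed, a PANSS of exactly 90 belongs to neither severity stratum. A regimen of one typical and one atypical agent, which inclusion criterion 4 does not exclude, has no stated class. These affect few patients and bias nothing.

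The cost is two degrees of freedom for the main effects and a line or two of text. Both factors are already collected, and if neither is prognostic the loss is under half a point of power.

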Specific Aim #3:Establish the time needed to reach peak efficacy. Duration of treatment in the original study was three weeks, and significant therapeutic benefit was observed only at the three-week endpoint but not earlier. In the proposed study, subjects will receive study drug for 6 weeks and we expect that the size of the therapeutic benefit of oxytocin will increase from 3 to 6 weeks.

Specific Aim # 4: Investigate the possible cognitive effects of intranasal oxytocin. In the pilot study, oxytocin significantly improved short term recall performance in the California Verbal Learning Test. This raises the possibility that chronic oxytocin will improve cognitive deficits associated with schizophrenia. This study will test this hypothesis using the Computerized Multiphasic Interactive Neurocognitive DualDisplay™ System (CMINDS®) and Mayer-Salovey-Caruso Emotional Intelligence Test: Managing Emotions (MSCEIT™ ME).

Specific Aim #5: To determine if daily intranasal oxytocin is sufficiently safe, feasible and acceptable to patients to warrant further clinical development. Information derived from this study will inform development of oxytocin not only for schizophrenia but other potential neuropsychiatric disorders.

Specific Aim #6: The objective of the study is to compare the efficacy of intranasal oxytocin versus intranasal placebo to improve symptoms in schizophrenia patients who have residual symptoms despite being on adequate treatment with antipsychotic medication. Improvement will be measured by total score in the Positive and Negative Syndrome Scale (PANSS).

Specific Aim #7: To determine if oxytocin-induced enhancement of mu-rhythm suppression of 'mirror' neurons in schizophrenia patients can serve as a predictive biomarker of individual clinical response to this neurohormone.

Secondary objectives include:

 To evaluate the efficacy of intranasal Oxytocin as measured by change in the total CGI-Severity and Improvement scores

- To evaluate the efficacy of intranasal Oxytocin as measured by change in the total GAF score
- To evaluate the efficacy of intranasal Oxytocin as measured by change in the total scores of HAM-A.
- To evaluate the efficacy of intranasal Oxytocin on self-rated social anxiety as measured by change in the total Social Phobia Inventory (SPIN).
- To evaluate the efficacy of intranasal Oxytocin as measured by change in the total Calgary Depression Scale for Schizophrenia (CDSS) scores.

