9. RESEARCH DESIGN AND METHODS

OVERVIEW:

The proposed study is a randomized, double-blind, placebo-controlled study of the value of adjunctive intranasal oxytocin added to existing antipsychotic treatment compared with adjunctive placebo in subjects with schizophrenia. Enrolled subjects will be randomized and receive 6 weeks of treatment with one of the following adjunctives to a stable antipsychotic regimen: 1) intranasal oxytocin (84 IU/day), intranasal oxytocin (168 IU/day) or intranasal placebo. The study will be conducted over 2 years. Approximately seventy-one subjects will be entered into the study, on average 35/36 at each site each year.

PRIMARY OUTCOME MEASURE:

Positive and Negative Syndrome Scale (PANSS): The three subscales of the PANSS include the Positive scale (7 items), the Negative scale (7 items), and the General Psychopathology scale (16 items). The total PANSS score is the sum of all 30 items of which each item is scored on a 1-7 rating system (7 indicating the worst symptoms). The items on the PANSS focus on symptoms that are common in patients with psychotic disorders and include hallucinations, delusions and disorganization as well as mood disturbances.

SECONDARY OUTCOME MEASURES WILL INCLUDE:

Global Assessment of Functioning (GAF): The GAF considers psychological, social, and occupational functioning on a hypothetical continuum of mental health illness. Scores on the GAF range from 1 (extremely severe) to 100 (superior functioning).

Clinical Global Impression-Severity of Illness (CGI-S): The CGI-S is used to evaluate changes in overall severity of illness. Scores range from 1 (not at all) to 7 (among the most extremely ill).

Clinical Global Impression-Global Improvement (CGI-I): The CGI-I is a global assessment to evaluate the subject's improvement or worsening from baseline. Scores on the CGI-I scale range from 1 (very much improved) to 7 (very much worse)

Calgary Depression Scale for Schizophrenia (CDSS) is a ten item diagnostic questionnaire intended to assess the severity of depression symptoms experienced by a given patient. The CDSS will be administered by a trained and qualified rater at each scheduled study visit.

Hamilton-Anxiety Scale (HAM-A): The HAM-A is a clinician administered scale for the evaluation of anxiety symptoms. The HAM-A consists of 14 items of which each item is scored 0 (not present) to 4 (very severe).

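### CGI-I is itself a rating of change, yet it goes through the same baseline-adjusted change-score model as PANSS, with no baseline of its own to adjust for

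*Combined protocol and SAP*

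**What the plan says.** Section 9, Secondary Outcome Measures, defines the two scales differently. On improvement: "The CGI-I is a global assessment to evaluate the subject's improvement or worsening from baseline". On severity: "The CGI-S is used to evaluate changes in overall severity of illness". Both run from 1 to 7, but only severity can be rated before treatment.

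Section 9, Analysis Methods, sets the primary analysis as the week-6 change in total PANSS, oxytocin groups combined against placebo, "with adjustment for baseline score using a likelihood-based mixed-effects model for longitudinal data analysis (MMRM LDA". The next paragraph lists the secondary measures, among them "CGI-S, CGI-I HAM-A, CCDS, GAF, cognitive scales as with the primary endpoint using the same MMRM LDA analyses". CGI-I gets no exception and no covariate of its own.

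The secondary objectives in section 6 describe the endpoint as "change in the total CGI-Severity and Improvement scores".

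The Study Procedures schedule has one row for HAM-A, CDSS, CGI-S, CGI-I and GAF, marked at Baseline and at weeks 1 to 6. A footnote to that row says CGI-S is rated twice at Baseline, before the dose and again at least 50 minutes after it. No footnote covers CGI-I.

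The Missing Data paragraph leaves further model detail to a Statistical Analysis Plan. The supplied text contains nothing more on CGI-I.

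**The concern.** A model that subtracts a baseline and adjusts for it suits a scale measured before and after treatment. CGI-I is a judgement made by looking back to baseline, so subtracting a baseline CGI-I gives a change in a change rating. Adjusting for it uses a covariate that should carry little or no information about later outcome.

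Read literally, the plan leaves the analyst to decide, once data exist, whether to use the observed score or a difference and which covariate to include. It also does not name the one covariate that is natural for CGI-I and already collected, the pre-dose CGI-S. At stake are the interpretability and precision of one named secondary efficacy measure in a trial planned at 24 placebo and 48 oxytocin patients.

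**Working it through.** The plan gives no figure for this point, so there is none to reproduce. The check is algebra plus a simulation of a single-visit linear model, not the full repeated-measures model: 24:48 allocation, 4,000 runs, within-arm SD 1, true difference -0.5. Correlations are assumed, since the documents give none.

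**Notation.** Y is CGI-I at a post-baseline visit, B a CGI-I recorded at the Baseline visit, T treatment, S the pre-dose CGI-S, and r the correlation of Y with S.

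**Step 1: does the subtraction matter?** The model as written is Y - B = a + tT + bB + e. Moving B across gives Y = a + tT + (b + 1)B + e. The treatment effect t and its standard error are the same; only the coefficient of B shifts by 1. With B in the model, computing change therefore costs no precision.

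**Step 2: what does B do as a covariate?**

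| Baseline-visit CGI-I | Consequence |
|---|---|
| Constant (such as 4) | Collinear with the intercept. The estimate equals the unadjusted one (largest simulated difference 1.8 × 10⁻¹⁵). |
| Arbitrary, unrelated to outcome | Expected variance factor 1 + 1/(72 - 4) = 1.015. Simulated: 1.014, 1.019, 1.015. |
| Blank | Neither the difference nor the covariate exists; the model cannot be fitted as written. |
| Rated after the in-clinic dose | A post-randomisation value; adjusting for it could remove part of the treatment effect. |

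The last case depends on timing. Randomisation and the first supervised dose both fall within the Baseline visit. The dispensing paragraph puts that dose after the visit's procedures, which suggests a pre-dose rating. However, CGI-S and most self-rated scales are repeated afterwards, and nothing times CGI-I.

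**Step 3: what would S add?** Residual variance falls to (1 - r²) of its unadjusted value.

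| Assumed r | 1 - r² | Simulated ratio | Standard error ratio, √(1 - r²) |
|---|---|---|---|
| 0.2 | 0.96 | 0.966 | 0.980 |
| 0.3 | 0.91 | 0.894 | 0.954 |
| 0.4 | 0.84 | not run | 0.917 |
| 0.5 (check only) | 0.75 | 0.752 | 0.866 |

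For r of 0.2-0.4, residual variance falls by 4-16% and the standard error by about 2-8%. Estimating the extra coefficient gives back about 1.5% (the factor 1.015 above), so the gain vanishes at r² = 1/69, r = 0.12. The average treatment estimate did not move (-0.495, -0.502 and -0.501 with S in the model, against -0.495, -0.501 and -0.499 without).

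**Step 4: where in the range?** Inclusion criterion 6 reads "Have a Clinical Global Impressions-Severity (CGI-S) scale score of at least 4 (moderately ill) at baseline". Restricting the range of S tends to lower r, so the lower end is more plausible.

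**The case against.** The strongest reply is that no sentence tells the analyst to adjust CGI-I for baseline CGI-I. The baseline score is named only for PANSS, CGI-I appears in a one-sentence list, and details are deferred to a further document. The shared schedule row is weak evidence too: it carries a single Baseline mark although CGI-S is rated twice there, and the self-rated row carries a double mark although ASEX is not repeated. The section 6 phrase covers two scales loosely.

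Part of this stands. The adjustment is inferred from applying the same model, and the Baseline mark alone does not prove that a baseline CGI-I will be used. But the sentence names CGI-I and sends it through the primary model without exception, the objective also speaks of change, and no supplied text corrects either. The stated rule does not fit the measure.

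A reader might go further in three ways that the documents do not support:

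- **That subtracting a noisy baseline inflates the variance.** It roughly doubles (simulated 1.95-2.05, with noise SD set equal to outcome SD) only for a change score without the baseline covariate. The plan includes that covariate, so the cost is about 1-2%.
- **That the CGI-I comparison is biased or its type I error inflated.** Randomisation protects it if the baseline value is constant or arbitrary. Only a post-dose covariate would threaten it, and the documents do not say the rating is made then.
- **That a Baseline CGI-I is bound to be worthless and can be deleted at no cost.** If rated after the supervised dose it could capture an acute response.

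**Conclusion.** The point holds as a minor one. A rating of change is assigned a baseline-adjusted change-score model for which it has no meaningful pre-treatment value. Depending on what is recorded at Baseline, the adjustment is inert, costs about 1-2% in variance, cannot be carried out, or conditions on a post-randomisation value.

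The gain from pre-dose CGI-S is about r² of residual variance. The 4-16% figure rests wholly on the assumed r of 0.2-0.4, and the CGI-S entry threshold makes the lower part more likely. CGI-I is one of several secondary measures analysed without multiplicity adjustment. The primary analysis and the sample size are not affected.

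**What to change.** - **Analysis Methods.** State that the observed CGI-I score at Visits 3-8 is analysed by MMRM with pre-dose Baseline CGI-S as covariate. Specify pre-dose, because CGI-S is rated twice at that visit. State also that no change in CGI-I is computed and that no Baseline-visit CGI-I enters the model.
- **Section 6 objective.** Reword it to change in CGI-S and the observed CGI-I score.
- **Schedule.** Either remove CGI-I from the Baseline column, or label it as a post-dose acute rating kept out of this model. The second option suits a team that wants the acute response.

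The cost is one or two sentences of text and one schedule mark or footnote. The covariate is already collected, so no assessment is added.
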